### *Dosing and IMP Administration*

Drug/placebo therapy starts the same day after the ablation procedure. A 3-month supply will be provided to all participants. Dronedarone 400mg or an oral placebo tablet will be administered twice daily (morning and evening) along with substantial meals. No dosing adjustment is needed in cases of mild renal impairment. Any adjustment to treatment would be considered a secondary endpoint and will not prompt an interruption in subsequent follow-up visits and assessments. Study participants will continue to be followed for primary and other secondary endpoints.

### **3-Month Visit**

Sites will collect vital signs, weight, and blood samples for labs. During this on-site visit, study participants will complete the second set of AFEQT and AFSS questionnaires. Sites will review and document any changes within the medical history, current and concomitant medication use, and presence of any adverse events. Study participants will also receive another CMR. At this time, study participants may also receive some or the rest of the IMP or placebo (9-month supply) depending upon their enrollment date. This is to ensure that no patient receives drug that is about to expire and new drug (with increased expiration date) in the same visit. Also, while on site, study participants may work with the study team to troubleshoot research devices and ask any questions if needed. At this time, their six-month and nine-month visit/phone-calls will be scheduled. Any leftover drug will be provided to a research member at this time for suitable disposal.

### **6-Month and 9-Month Visits/Phone Calls**

Similar to the 3-month visit, sites will review and document any changes within the medical history, current and concomitant medication use, and presence of any adverse events. Sites may also work with study participants to troubleshoot devices and address any questions or concerns. Sites will also check on medication adherence as well as discuss how study participants are managing with their medication supply. Sites may need to supply the rest of the IMP or placebo during these time points (scheduled/unscheduled visits) depending on enrollment date. This is to ensure that no patient receives drugs that are about to expire. Any leftover drug will be provided to a research member at this time for suitable disposal.

### **12-Month Visit**

The 12-month visit is the same as the 3-month visit. Sites will collect vital signs, weight, and blood samples for labs. During this on-site visit, study participants will complete their final AFEQT and AFSS questionnaires, discuss any changes in their medication and review any adverse events. Study participants will also receive their final CMR scan. If any questions or concerns arise related to the study devices, these can be addressed at this visit. Any leftover drug will be provided to a research member at this time for suitable disposal.

## **End of Trial (EoT) Visit Phone Call**

A phone call will be scheduled towards the end of the clinical trial (around 13 months). Sites will review and document any changes within the medical history, current and concomitant medication use, and presence of any adverse events

## **Study Schedule**

---

### **Screening Visit**

- Obtain and document signed Informed Consent Form and HIPAA Authorization Form.
- Review medical history to determine eligibility based on the inclusion/exclusion criteria.
- Obtain patients demographic information.
- Complete Physical Examination
- Collect anthropometric data (height and weight), and vital signs
- Assessment of medication/concomitant therapy.
- ECG reading.
- Schedule baseline CMR prior to ablation procedure.

### **Baseline CMR Visit (Day -90 to 0)**

- Verify inclusion/exclusion criteria.
- Document study eligibility has been verified by site investigator signature.
- Confirm medication/ concomitant therapy.
- Collect weight and vital signs.
- Obtain baseline CMR scan.
- Blood draw to obtain baseline creatinine levels, hepatic panel as well as biomarkers for fibrosis and inflammation.
- Obtain baseline AFEQT online questionnaire.
- Obtain baseline AFSS online questionnaire.
- Determine that the baseline scan meets standard requirements for enrollment.

### **Ablation Procedure (Day 0)**

- Confirm medication/ concomitant therapy.
- Perform cardiac ablation (SOC).
- Collect weight and vital signs
- Determine that cardiac ablation was successful (i.e. well tolerated by patient)- requirement for enrollment
- Stratify and randomize into treatment arms (1:1 ratio).
- Dispense dronedarone or placebo (3-month supply) according to randomization assignment.
- Provide patient with ECG monitoring device

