### *Randomization*

Patients who meet the eligibility criteria will be randomly assigned in a 1:1 ratio (i.e. 50/50 chance of being assigned to either study arm). An Interactive Web Response System (IWRS) randomization software program will be used to assign each study participant to a study arm. Before randomization occurs, each study participant will be stratified by age (i.e. <65 years old and  $\geq$ 65 years old) and AF type (i.e. persistent and paroxysmal). Once randomization occurs, each study participant will also be assigned a participant ID number.

Randomization will occur after cardiac ablation for two major reasons. First, we want to make sure that each enrolled participant has recovered well from the procedure prior to randomization. Secondly, site investigators may desire to perform more lesions during ablation if they are aware of how the study participant was assigned (e.g. unconscious bias). Therefore, to minimize bias and to maximize balance across groups, study participants will be randomized after cardiac ablation.

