### *Medical Assessment*

Study participants will be asked about their medical history and current medication use. Anthropometric measures (e.g. height and weight) and vital signs such as blood pressure and heart rate will be assessed as part of the inclusion/exclusion criteria assessment. A complete physical examination will be performed during this time.

If an ECG for the patients has been taken within one month of enrolment, these patients do not require a repeat ECG reading at the Screening Visit and results will be recorded accordingly. Monitoring of vitals will also be performed at baseline and prior to each in person follow-up visit to provide close monitoring for patient safety.

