### **Day of Cardiac Ablation**

After the baseline visit, patients will be scheduled for a cardiac ablation. Clinical investigators will schedule ablation procedures within 90days after CMR imaging has been completed.

Patients will be medically assessed by the site investigator. Patients who are deemed by the site investigator to have not tolerated the ablation well will not be enrolled in the study. Due to current hospital SOC, patients may be discharged up to 24 hours after ablation. Discharge may be expedited per physician discretion and other hospital-based policies (e.g. COVID-19, etc.).

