### **1 INDICATIONS AND USAGE**

® MULTAQ is indicated to reduce the risk of hospitalization for atrial fibrillation in patients in sinus rhythm with a history of paroxysmal or persistent atrial fibrillation (AF) [see *Clinical Studies (14)*].

Page 41 of 49

Version 4.0:  
Revision Date: April 27th, 2022

Copyright© April 2022 Tulane University School of Medicine, Academic Research Organization on behalf of the Principal Investigator.  
All rights reserved.

TULANE UNIVERSITY  
Academic Research Organization

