## **5.3 Increased Risk of Stroke in Permanent AF**

In a placebo-controlled study in patients with permanent atrial fibrillation, dronedarone was associated with an increased risk of stroke, particularly in the first two weeks of therapy [*see Clinical Studies (14.4)*]. MULTAQ should only be initiated in patients in sinus rhythm who are receiving appropriate antithrombotic therapy [*see Drug Interactions (7.3)*].

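### Dronedarone starts on the day of ablation with no requirement for sinus rhythm or antithrombotic therapy, although the protocol's own label text asks for both

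*Combined protocol and SAP*

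**What the plan says.** Appendix C, section 5.3, states the starting condition: "MULTAQ should only be initiated in patients in sinus rhythm who are receiving appropriate antithrombotic therapy". Section 1 of the same appendix gives the indication as reducing hospitalisation for AF "in patients in sinus rhythm with a history of paroxysmal or persistent atrial fibrillation".

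The body of the protocol sets the timing under Dosing and IMP Administration: "Drug/placebo therapy starts the same day after the ablation procedure". The list under Ablation Procedure (Day 0) contains a medication step, "Confirm medication/ concomitant therapy", then the ablation, weight and vital signs, and this requirement: "Determine that cardiac ablation was successful (i.e. well tolerated by patient)- requirement for enrollment". Randomisation, dispensing and issue of the wearable monitor follow. The list contains no ECG.

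The Schedule of Events marks the ECG at screening only. Medical Assessment allows an existing tracing to stand in for it: "If an ECG for the patients has been taken within one month of enrolment, these patients do not require a repeat ECG reading". The section Day of Cardiac Ablation adds: "Clinical investigators will schedule ablation procedures within 90days after CMR imaging has been completed". The CMR Protocol section prefers a gap of 30 days or less.

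**The concern.** Persistent AF is an eligible type and a randomisation stratum, so a patient still in AF after the procedure is foreseeable. A site that follows the protocol exactly could randomise that patient and give dronedarone the same day, contrary to the label text the protocol reproduces. The same holds for a patient in sinus rhythm who is not on antithrombotic therapy. Section 5.3 reports that the excess of strokes was greatest early in treatment, so the first dose is the natural point for a check.

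Trial conduct is also affected. Investigators know the assignment (Blinding section). If rhythm is left to their judgement after randomisation, they have a reason to delay or cardiovert in the dronedarone arm and none in the placebo arm. Cardioversion is a secondary endpoint. A condition applied before assignment avoids that asymmetry.

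**Working it through.** No sample-size or power figure is involved. The check sets the label condition beside each place where the protocol could impose it.

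| Place | What it does | Sinus rhythm required at first dose? | Antithrombotic therapy required? |
|---|---|---|---|
| Inclusion Criteria | Age, and paroxysmal or persistent AF undergoing ablation | No | No |
| Exclusion Criteria, item 2 | Excludes those who cannot or will not be cardioverted before ablation | No | No |
| Exclusion Criteria, dronedarone contraindications | Through Appendix C section 4, reaches AF in which sinus rhythm will not or cannot be restored | No | No |
| Concomitant Medications | Lists prohibited drugs; medication use assessed at every timepoint | No | No |
| Biological Samples | PT/INR and PTT on the laboratory list | No | No, a test result is not a treatment rule |
| Day of Cardiac Ablation | Investigator assesses the patient; gate is tolerance | No | No |
| Ablation Procedure (Day 0) | Medication confirmed; gate is tolerance | No | No |
| Schedule of Events, Day 0 column | Medication review and vital signs, no ECG | No | No |

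The condition in section 5.3 sits among the warnings and not in the list of contraindications in section 4. The exclusion for contraindications therefore does not bring it in. It does bring in permanent AF, and the dronedarone risk section of the protocol says the same.

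Age of the scheduled ECG at first dose:

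- Take the screening ECG and the baseline CMR on the same day.
- Ablation may follow the CMR by up to 90 days, and dosing is on the day of ablation.
- ECG age at first dose = 0 + 90 = about 90 days. At the preferred spacing it is 0 + 30 = about 30 days or less.
- No maximum is stated between screening and CMR, so the 90 days assumes that interval is zero.

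What is recorded on Day 0: the Medication(s) Review row in the Schedule of Events is marked for the day of ablation, in line with the Day 0 list and the Concomitant Medications section. Anticoagulant use at the first dose should therefore be recoverable from study records. Nothing equivalent is scheduled for rhythm.

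**The case against.** The case on the other side has substance. The stroke warning is headed as concerning permanent AF, and those patients are already excluded. Section 5.2 of Appendix C foresees patients being in AF while on the drug: it advises cardioversion if indicated, or stopping, with rhythm monitoring at least every 3 months. The trial's 30-day wearable periods from discharge and at 3, 6, 9 and 12 months fit that, and patients are told to seek care for positive readings or symptoms. Sites will often know the rhythm and give anticoagulation as routine care around ablation.

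All of this lowers the likely consequence. None of it is a condition before the first dose. The wearable is issued at the end of the Day 0 list, and patients are told its strips are not read in real time. The starting instruction is not worded as limited to permanent AF.

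Some stronger readings are tempting but not supported:

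- A reader might infer that permanent AF is admitted. It is excluded.
- A reader might infer that antithrombotic use goes unrecorded. It is covered by the Day 0 medication review; what is missing is a requirement.
- A reader might add the one-month substitution to the 90 days and get about 120. That takes enrolment in Medical Assessment to mean the screening visit. The Day 0 text places enrolment after ablation, and on that usage a substituted tracing is at most about 30 days old.
- A reader might put a count on it. At an assumed 2% to 10% in AF after ablation, 330 × 0.02 = 6.6 and 330 × 0.10 = 33 patients, half of them (3.3 to 16.5) on dronedarone. The documents give no source for that range, so the count is illustration only.
- A reader might infer lost power from AF present at time zero. The documents do not settle whether the assumed 50% control recurrence already includes such events, so no loss can be claimed.

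**Conclusion.** The point holds in a narrow form. Of the two conditions the label text sets for starting dronedarone, the protocol requires neither before randomisation or the same-day first dose. What remains after the existing safeguards is (a) no documented rhythm check before dosing, which matters for patients in AF whose rhythm might still be restored, and (b) no rule that antithrombotic therapy must be in place.

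The only firm number is the possible age of the scheduled ECG, about 90 days when the CMR-to-ablation window is fully used. The number of patients affected is not known from the documents. Nor is the size of the risk in this population, because the stroke data in section 5.3 come from permanent AF. The case rests on safety and on consistency with the protocol's own appendix, and on the protocol text as written. Routine site practice may close much of the gap without the protocol saying so. The change should be made, but this is not a reason to doubt the trial's primary comparison.

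**What to change.** In Ablation Procedure (Day 0) and the Schedule of Events, extend the existing post-ablation tolerance check. Document the rhythm on a post-procedure ECG before randomisation. Randomise and dispense only if the patient is in sinus rhythm, after cardioversion if needed, and the Day 0 medication review confirms appropriate antithrombotic therapy. Add one sentence to the dronedarone risk section stating that both are verified before the first dose.

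The Randomization section already gives this reason for randomising after the procedure: "First, we want to make sure that each enrolled participant has recovered well from the procedure prior to randomization". The new condition sits at the same point and applies equally to both arms. The same tracing would also refresh the QTc, PR and bradycardia exclusions, for which the only scheduled ECG is also at screening.

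The cost is one short ECG and a rhythm field per patient, plus an amendment needing IRB approval. Some patients may need cardioversion before same-day dosing, which can delay discharge. Some will not be randomised after they have had the baseline CMR and ablation. That number is probably small but cannot be derived from the documents for either condition. Patients whose rhythm cannot be restored are already barred by the contraindication.

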## **Exclusion Criteria**

---

Patients will be excluded from enrollment if any of the following criteria are present:

1. Any health-related gadolinium/MRI contraindications (e.g. allergy to gadolinium or similar agent, pacemakers, Implantable Cardioverter Defibrillators (ICD's), other devices/implants contraindicated for use of MRI, etc.)
2. Patients who are medically ineligible to be or are unwilling to be cardioverted electrically or by medications before ablation.

---

 “Paroxysmal” atrial fibrillation (AF) is defined here as an AF episode lasting within 7 days of onset and spontaneously resolving without the need for a pharmacological or electrical cardioversion. “Persistent” atrial fibrillation is defined here as any AF episode lasting beyond 7 days or any episode 7 days or less requiring a pharmacological or electrical cardioversion to terminate the abnormal rhythm.

3. Patients who have a known terminal illness with a prognosis less than 12 months at the time of the informed consent process.
4. Patients who are unable to or are unwilling to receive cardiac MRI (CMR) scans.
5. Patients who are incarcerated or become incarcerated during the trial period.
6. Patients who are unable or are unwilling to return to the study site/clinic for follow-up procedures such as, collecting IP/Placebo, collecting devices, blood draws
7. Patients who have not successfully recovered from cardiac ablation.
8. Patients who do not meet quality standards for the baseline CMR scan
9. 8. Patients weighing >300 lbs. as CMR quality may decrease with patients with increased BMI. Patients that have contraindications to dronedarone. (This includes patients with decompensated heart failure or New York Heart Association (NYHA) Class IV, second or third-degree atrioventricular (AV) block or sick-sinus syndrome [except when used in conjunction with a functioning pacemaker]), concomitant use of strong CYP-3A inhibitors or other Class I or III AADs, drugs or herbal products that prolongs the QT interval and may induce Torsade de Pointes.
10. Liver or lung toxicity related to previous use of amiodarone, severe hepatic impairment including any stage of cirrhosis, acute liver failure, and/or interstitial lung disease including pulmonary fibrosis and pneumonitis.
11. Symptomatic bradycardia <50bpm, QTc Bazett interval  $\geq$ 500ms or PR interval >280ms,

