## **Adverse Events (AEs) and Serious Adverse Events (SAEs) Related to the EDORA Trial**

### ***a) Cardiac Ablation***

Cardiac ablation is standard of care. Patients who have attempted to control their arrhythmia via AADs with no positive outcome and/or have suffered serious side effects from certain medications are advised to undergo this procedure. Most symptoms or side effects related to cardiac ablation are not from the procedure itself. Patients may complain of back ache from lying on the operation table for a longer time. Sore throat is a common side effect of the procedure due to the anesthetic use during intubation and some arrhythmia may be experienced afterwards (blanking period).

Direct effects of cardiac ablation include bleeding or infection at the site where the catheter was inserted, puncturing of the heart, damage to heart valves, damage to the heart's electrical system, which could worsen the arrhythmia and require a pacemaker to correct. In addition, venous thromboembolism, pulmonary vein stenosis, stroke or heart attack could occur. Renal damage from contrasting dye used during the procedure, and even death may occur in rare cases.

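### No ECG is required between ablation and randomization, so the AV-block, PR and QTc exclusions for dronedarone rest on a screening tracing that can be 90 days old or more

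*Combined protocol and SAP*

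**What the plan says.** **Criteria.** Under Exclusion Criteria, the item on contraindications to dronedarone (printed as 9) bars "second or third-degree atrioventricular (AV) block or sick-sinus syndrome", with an exception for a functioning pacemaker. Item 11 bars QTc Bazett of 500 ms or more and PR above 280 ms. Appendix C, section 4, lists the same conditions as contraindications.

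**When they are checked.** The Screening Visit list includes an ECG reading, and the ECG row of the Schedule of Events is marked in that column only. Medical Assessment lets an earlier tracing stand in: "If an ECG for the patients has been taken within one month of enrolment, these patients do not require a repeat ECG reading". The investigator's sign-off belongs to the baseline CMR visit, before ablation: "Document study eligibility has been verified by site investigator signature". The inclusion/exclusion row of the Schedule of Events is marked at screening only.

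**Day 0.** The section Day of Cardiac Ablation states: "Clinical investigators will schedule ablation procedures within 90days after CMR imaging has been completed". It also provides for a medical assessment by the investigator. The Day 0 list sets one condition after the procedure, "Determine that cardiac ablation was successful (i.e. well tolerated by patient)- requirement for enrollment", followed by randomization and dispensing. Dosing and IMP Administration adds: "Drug/placebo therapy starts the same day after the ablation procedure".

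**Monitoring.** Under Primary Endpoints, monitoring for recurrence begins at discharge, usually 24 to 48 hours after ablation.

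**The concern.** PR and QTc can be read only from an ECG, and AV block without symptoms or a slow pulse is also found that way. The tracing used for eligibility is recorded before a procedure that the protocol lists as able to injure the heart's "electrical system, which could worsen the arrhythmia and require a pacemaker to correct". A patient can pass at screening, leave the ablation with a PR above 280 ms or a silent second-degree block, be judged to have tolerated the procedure, and be randomized to a drug that is contraindicated for that finding. Every step would follow the plan as written.

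Two things are at stake. The first is safety. The second is the analysis set: a patient whose contraindication is found after randomization should not stay on dronedarone but remains in the intention-to-treat population. Site investigators know the assignment, so a conduction finding looked for after randomization could be pursued differently in the two arms. A check before randomization avoids both problems and treats the arms alike.

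**Working it through.** The documents give no figure for the age of the ECG at first dose, so there is none to reproduce. The check is a day count and a comparison of the Day 0 list with the criteria.

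**1. Age of the qualifying ECG at first dose**

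Age = S + C + P, where
- S = screening to baseline CMR visit: 0 days or more, with no upper limit stated;
- C = baseline CMR to ablation: 0 to 90 days (Baseline CMR Visit; Day of Cardiac Ablation), preferably within 30 (CMR Protocol);
- P = allowance for an earlier ECG: 0 to about 30 days (Medical Assessment), if enrolment there means the screening visit.

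| Case | S + C + P | Age |
|---|---|---|
| CMR at the preferred limit, ECG done at screening | 0 + 30 + 0 | 30 days |
| CMR at the outer limit, ECG done at screening | 0 + 90 + 0 | 90 days |
| CMR at the outer limit, earlier ECG reused | 0 + 90 + 30 | about 120 days |

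Any gap between screening and the CMR visit adds to these. If enrolment means Day 0, a reused ECG is at most about a month old, but one recorded at the screening visit can still be 90 days old or more. When the visits fall close together, the age is short.

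**2. What Day 0 can show**

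The list has seven items: medication review, ablation, weight and vital signs, the tolerance judgement, randomization, dispensing, and handing over the monitor. Items naming PR, QTc or AV conduction: 0 of 7.

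| Criterion | Could Day 0 as written reveal it? |
|---|---|
| Second- or third-degree AV block | If symptomatic or bradycardic, yes, through heart rate or the investigator's assessment; if silent, no |
| Sick sinus syndrome | As above |
| PR above 280 ms | No |
| QTc Bazett of 500 ms or more | No |

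**3. Whether the wearable fills the gap**

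Dosing is twice daily. Doses taken before monitoring starts:
- first dose on the day of ablation, discharge at 24 to 48 hours: 2 × 1 to 2 × 2 = 2 to 4;
- discharge within 24 hours (Day of Cardiac Ablation): up to 2;
- drug first given at discharge (as Treatment Groups can be read): 0.

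Even with 0 doses the monitor follows randomization. The device section says strips are not read in real time and mentions no PR or QTc output. The vendor's alert for critical rhythms may catch high-grade block, but only once the device is worn.

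**The case against.** The best defence is that a gate already exists. Randomization was placed after ablation partly to confirm recovery, exclusion 7 removes patients who have not recovered, the investigator assesses the patient on the day, and only eligible patients may be randomized. Investigators are unblinded for safety reasons and can act on any routine post-procedure tracing. This is largely right, and it narrows the point: a reader might infer that nothing on Day 0 could reveal a conduction problem, and that goes too far. What survives is that recovery is defined by tolerance, and no measurement is specified that would show a silent PR, QTc or AV-conduction change. Whether sites routinely record an ECG after ablation is not in the documents.

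Three stronger readings are tempting but unsupported.

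- **AF on Day 0 as a contraindication.** Appendix C, section 5.3, says "MULTAQ should only be initiated in patients in sinus rhythm who are receiving appropriate antithrombotic therapy". A reader might infer that a patient in AF receives a contraindicated drug and must stop it. Section 4 contraindicates permanent AF only, and section 5.2 allows cardioversion, if clinically indicated, as an alternative to stopping. The sentence is a warning in the insert, not a criterion in the protocol body. Requiring sinus rhythm would add a new entry criterion, could lower the recurrence event count, and, through cardioversion and re-checking, would affect a secondary endpoint.
- **Earlier antiarrhythmics.** Class I and III drugs may be stopped as late as 24 hours before first dose, so the screening ECG may reflect another drug. The protocol classes these as QT-prolonging, so for QTc such a tracing would tend to err toward exclusion, not false reassurance.
- **Ninety days as typical.** It is the far end of a window whose preferred limit is 30 days.

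**Conclusion.** The point stands in a limited form. The plan carries explicit ECG exclusions but specifies no ECG after the procedure most likely to change them and before a same-day start of treatment. The qualifying tracing can be 90 days old or more. The conclusion rests on the visit lists and the Schedule of Events being complete, and on sites doing no more than they require. Where a post-procedure ECG is already routine, the change mainly ties that tracing to randomization.

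The documents give no rate of post-ablation AV block or prolonged PR or QTc, so no patient count can be given. The stated sample size and power are unaffected. The change should be made as an inexpensive safety and eligibility correction. The gap does not undermine the primary analyses.

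**What to change.** In the Day 0 list, ahead of the stratification and randomization item, add: *Review a 12-lead ECG recorded after ablation (a standard-of-care tracing may serve) and randomize only if the ECG parts of exclusions 9 and 11 are not met.* Mark the ECG row of the Schedule of Events under Day of Cardiac Ablation. The qualifying tracing is then from the same day.

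The insert's sinus-rhythm warning can be left to the investigator reading the tracing. No change to the recurrence endpoint is proposed.

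**Cost.** At most one ECG per patient reaching this step, fewer where a routine tracing serves, and no new visit. A few patients may be ablated but not randomized. That share is not in the documents. At an assumed 1%, 2% or 5%, randomizing 330 needs 330/0.99 = 333.3, 330/0.98 = 336.7 or 330/0.95 = 347.4 ablated patients, that is 334, 337 or 348 (4, 7 or 18 more). The intention-to-treat set is unaffected because the check precedes randomization.
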